#### 5.4.4.2. Tremelimumab Dose Reductions

Changes in the dose levels for tremelimumab will be discussed with the sponsor. For cohorts where PrCa VBIR will be administered alone, dose reduction of tremelimumab by 1 dose level may be allowed depending on the type and severity of toxicity encountered. For cohorts where PrCa VBIR will be given in combination with PF-06801591, dose reductions of tremelimumab by 1 dose level will be allowed. In addition, an intermediate dose may be considered. Participants requiring a dose level lower than 40 mg will be discontinued from treatment and enter into the follow-up phase unless otherwise agreed between the investigator and sponsor. Algorithms for the management of suspected pulmonary, GI, liver, endocrine, skin, neurological and renal toxicities have been developed (See [Appendix 7](#)). All dose modifications/adjustments must be clearly documented in the participant's source notes and CRF.

Once a dose has been reduced for a given participant, all subsequent doses should be administered at that dose level, unless further dose reduction is required. Dose re-escalation for tremelimumab is not allowed.

If a participant experiences a Grade  $\geq 3$  toxicity or an intolerable side effect, withhold dosing for one week or until symptoms improve to Grade  $\leq 2$ , then resume at the same or a reduced dose (120 mg or 80 mg), if warranted.

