### **1.3.2. Safety and Part B Expansion Dose for PF-06753512 (PrCa VBIR) combined with PF-06801591 (anti PD-L1 antibody)**

As of 11 November 2019, 69 participants had been enrolled in the B7791001 study in Cohorts 1A and 2A (n=7), which include escalating doses of AdC68 (PF-06755992) ranging from  $4 \times 10^{11}$  VP to  $6 \times 10^{11}$  VP and a fixed dose of pDNA (PF-06755990) of 5 mg; Cohorts 3A (n=6) and 1B (n=20), which include  $6 \times 10^{11}$  VP AdC68, 5 mg of pDNA, and 80 mg of tremelimumab; Cohort 6A (n=7) and 5B (n=12), which include  $6 \times 10^{11}$  VP AdC68, 5 mg of pDNA, 80 mg of tremelimumab, and 130 mg of PF-06801591; Cohort 9A (n=3), which includes  $6 \times 10^{11}$  VP AdC68, 5 mg of pDNA, 40 mg of tremelimumab and PF-06801591

130 mg; and Cohort 7A (n=14), which includes  $6 \times 10^{11}$  VP AdC68, 5 mg of pDNA, 80 mg of tremelimumab and PF-06801591 300 mg.

As of 11 November 2019, the most frequently experienced ( $\geq 5$  participants) treatment related AEs were fatigue and influenza like illness (27 participants; 39.1% each), diarrhoea (14 participants; 20.3%), nausea and pyrexia (10 participants; 14.5% each), decreased appetite, and myalgia (9 participants; 13.0% each), injection site pain, alanine aminotransferase increased, headache, and amylase increased (8 participants; 11.6% each), aspartate aminotransferase increased, lipase increased, and arthralgia (7 participants; 10.1% each), pruritus (6 participants; 8.7%), hyperthyroidism, hypothyroidism, abdominal pain, chills, vomiting, injection site discomfort, weight decreased, and hyponatraemia (5 participants; 7.2% each).

Adverse Drug Reactions (ADRs) identified for PrCa VBIR (PF-06753512) in combination with PF-06801591 include colitis and hypothyroidism.

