### **1.6.3. Clinical Tremelimumab Dosing**

More than 1000 participants with cancer have been treated with tremelimumab as single-agent or in combination with another anti-cancer treatment. Clinical safety data for tremelimumab, at IV doses ranging from 0.01 to 15 mg/kg, indicate an acceptable safety profile in participants with cancer. The established maximum tolerated dose (MTD) for single-agent therapy is 15 mg/kg IV every 12 weeks, a dose level that has been extensively studied in a Phase 3 trial in participants with melanoma. Diarrhea, pruritus, and rash were the most common treatment-related adverse events (AEs) associated with tremelimumab. Another important event observed related to tremelimumab was hypopituitarism.

Monthly dosing, as planned for this study, was tested in the clinic in participants with melanoma, where administration of up to 10 mg/kg IV monthly was tolerated with no dose-limiting toxicity observed. The overall profile was found to be acceptable with the most frequent treatment-related AEs being diarrhea, rash, and pruritus. Frequency of Grade 3/4 AEs was 27% in the participants dosed with 10 mg/kg once every month.

The highest dose of tremelimumab will not exceed 150 mg, which equals to 2 mg/kg for a 75 kg patient, is expected to lead to a systemic exposure not exceeding that of a 2 mg/kg IV dose in a 75 kg patient. Thus, the AUC and Cmax of this dose are expected to be lower than those of the 10 mg/kg dose of tremelimumab previously administered to participants monthly via the IV route as described above.

Given the lower doses and the different route of administration, SC rather than IV administration, this study will start at a dose level of 80 mg total dose SC. In the event that 80 mg SC is not tolerated, lower dose levels (eg, 40 mg) may be tested.

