#### **3.4.1. Part B Expansion Dose: Participants with mCRPC (Cohort 3B)**

1. AdC68:  $6 \times 10^{11}$  VP administered IM.
2. pDNA: 5 mg administered IM with electroporation device.
3. Tremelimumab: 80 mg administered SC:
  - 3a. Tremelimumab dose may be decreased to 40 mg SC depending upon emerging safety data.
4. PF-06801591: 300 mg administered SC:

- 4a. PF-06801591 dose may be decreased to 130 mg SC depending upon emerging safety data.

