**Table 3. Tremelimumab Available Dose Levels**

Dose Level	Tremelimumab*
-1	40 mg
Starting	80 mg**

\* Intermediate doses may also be considered upon discussion with the sponsor.

\*\* Dose lower than 80 mg may be evaluated based on emerging safety data.

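### Protocol 5.4.4.2 names 120 mg and 80 mg as reduced tremelimumab doses although no described cohort exceeded 80 mg, and its re-treatment rule, Tables 4 and 6 and Appendix 7 disagree with no stated ranking

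*Protocol*

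**What the plan says.** **Dose.** Protocol 5.4.4.2, on a Grade ≥3 toxicity or an intolerable side effect, says to "withhold dosing for one week or until symptoms improve to Grade" ≤2, "then resume at the same or a reduced dose (120 mg or 80 mg), if warranted". The same section sets the floor: "Participants requiring a dose level lower than 40 mg will be discontinued from treatment", unless investigator and sponsor agree otherwise. Table 3 lists two levels, 80 mg (starting) and 40 mg (−1), and adds "Intermediate doses may also be considered upon discussion with the sponsor". Section 1.3.2 gives Cohort 7A as "5 mg of pDNA, 80 mg of tremelimumab and PF-06801591 300 mg" and Cohort 9A as "5 mg of pDNA, 40 mg of tremelimumab and PF-06801591" 130 mg. Sections 3.4.1 and 3.4.2 set the expansion dose at 80 mg, and both state: "Tremelimumab dose may be decreased to 40 mg SC depending upon emerging safety data".

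**Re-treatment.** Section 5.4.2 bars re-treatment until every listed criterion is met. For non-hematologic toxicity that is baseline or Grade ≤1, with Grade ≤2 open to the investigator's discretion if it poses no safety risk. Table 4 (regimens without PF-06801591) and Table 6 (regimens with it) carry separate rules by grade. A double-asterisk footnote to Table 6 allows resumption in some cases after discussion with the sponsor.

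**Immune-related events.** Appendix 7 gives algorithms for PF-06801591 and/or tremelimumab, including one for myasthenia gravis. Sections 5.4.4.2 and 5.4.4.3 point to Appendix 7 but do not say which text prevails. Table 6 is introduced as general rules from which case-by-case departures are possible.

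**The concern.** A site that follows the sentence in 5.4.4.2 literally finds two doses labelled as reductions, and neither lowers the dose of a participant on 80 mg. The one listed reduction, 40 mg, is not named there. The sentence also gives a route back to dosing that the tables close.

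For immune-related toxicity, a site can find one text allowing resumption and another requiring a permanent stop for the same event. These are not remote events. Section 1.3.2 reports, among 69 participants, treatment-related diarrhoea in 14, ALT increase in 8, AST increase in 7, and hyperthyroidism and hypothyroidism in 5 each (grades not given). It also names colitis and hypothyroidism as adverse drug reactions. The Document History entry for Amendment 5 says the myasthenia gravis algorithm was added because of an event seen in this study.

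Enrollment is closed (Section 3.1.2), but treatment continues through maintenance until progression, refusal or unacceptable toxicity (Section 3.1). The stake is therefore safe and uniform re-treatment of whoever remains on therapy.

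**Working it through.** **Step 1: has anyone been assigned more than 80 mg?** Section 1.3.2 gives counts at 11 November 2019: 7 (1A and 2A) + 6 (3A) + 20 (1B) + 7 (6A) + 12 (5B) + 3 (9A) + 14 (7A) = 69, which reproduces the stated 69. Tremelimumab was not given in 1A and 2A, was 40 mg in 9A, and was 80 mg in the rest. Later enrollment was Cohort 3B (18 participants) and the growth of 5B from 12 to 15, both at 80 mg. Nobody described received more than 80 mg.

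**Step 2: what the named doses amount to.** Change = named dose / assigned dose − 1.

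| Assigned dose | 120 mg | 80 mg | 40 mg (Table 3, level −1) |
|---|---|---|---|
| 80 mg | 120/80 − 1 = +50% | 80/80 − 1 = 0% | 40/80 − 1 = −50% |
| 40 mg (9A, n = 3) | 120/40 − 1 = +200% | 80/40 − 1 = +100% | 0% |

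Section 1.6.3 says "The highest dose of tremelimumab will not exceed 150 mg", but 120 mg would be a reduction only from a dose above 120 mg, and no described cohort had one.

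**Step 3: the resumption rule in the same sentence.**

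- Against Tables 4 and 6: for Grade 3 non-hematologic toxicity, where resumption is allowed, both require Grade ≤1 or baseline. At Grade 4 both say discontinue, subject in Table 6 to the double-asterisk footnote. Section 5.4.4.2 allows Grade ≤2, or simply one week, and does not except Grade 4. For Grade 3 hematologic toxicity the tables also use Grade ≤2, so that threshold agrees.
- Against Section 5.4.2: the clear conflicts are the one-week route, which as written needs no recovery at all, and the unconditional Grade ≤2.

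**Step 4: Table 6 against Appendix 7.** At least these differ:

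| Event | Table 6 with footnotes | Appendix 7 |
|---|---|---|
| Grade 3–4 AST, ALT or bilirubin | Discontinue, but may resume at Grade ≤1 or baseline after sponsor discussion | Permanent discontinuation |
| Grade 3 pneumonitis | Same; the permanent rule is printed for Grade >3 only | Permanent discontinuation |
| Grade 4 rash, Grade 4 creatinine, other Grade 4 irAE | Same as first row | Permanent discontinuation |
| Myasthenia gravis (not listed in Table 6) | Grade 2 continue; Grade 3 withhold, then resume; Grade 4 discontinue, subject to the footnote | Permanent discontinuation once clinically diagnosed |
| Grade 2 diarrhea | Continue; single-asterisk footnote requires persistence at Grade 3 before any modification | Withhold |
| Grade 2 other irAE | Continue if not a listed event | Withhold |
| Grade 2 primary endocrinopathy | Withhold | Continue |

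In the last row Table 6 is the stricter text; in the others Appendix 7 is. The endocrine difference does not extend to hypophysitis, where Appendix 7 also withholds for moderate or worse symptoms.

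**The case against.** **Practical effect of the dose error.** The strongest reply is that nobody is likely to receive 120 mg. Section 5.4.4.2 requires sponsor discussion of dose changes, speaks of a reduction by one level, and bars re-escalation. Section 3.1.1 says escalation within a patient was not permitted. This stands. A reader might infer from the percentages in Step 2 that participants face overdosing; the surrounding text does not support that. The percentages show that the sentence is wrong, not how large a risk it creates.

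**Section 5.4.2.** A reader might infer that 5.4.4.2 contradicts 5.4.2 throughout. It does not: 5.4.2 covers Grade 3 or 4 toxicity without excepting Grade 4, and it allows Grade ≤2 at the investigator's discretion. The Grade 4 conflict is with the tables only.

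**Table 6 and Appendix 7.** Much of Step 4 sets a permission, conditional on sponsor discussion, against a specific prohibition. A site that follows Appendix 7 breaches nothing, and a general table giving way to a specific algorithm is a natural reading. That softens the point, but no text states it, and it cannot settle the Grade 2 endocrine case, where the specific text is the looser one. Two wider readings also fail. The double-asterisk footnote does not reach myasthenia gravis at every grade: it reaches it only at Grade 4, and Grades 2 and 3 conflict through the cells for unlisted events. A first Grade 3 colitis is not in conflict as printed; it becomes so only if the footnote's Grade >3 is rewritten as Grade ≥3.

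**Letting Appendix 7 govern throughout.** This obvious remedy would loosen some safeguards. It would continue dosing at Grade 2 primary endocrinopathy. It would also drop the sponsor discussion before resuming after Grade 3–4 endocrinopathy, Grade 3 creatinine elevation or a first Grade 3 colitis. That part of the objection is right and shapes the fix.

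**Conclusion.** The point holds and should be fixed. The dose wording in 5.4.4.2 is wrong for every described participant, and its resumption route contradicts Tables 4 and 6 and, more narrowly, Section 5.4.2. Table 6 and Appendix 7 give different instructions for at least the events in Step 4, without a ranking.

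A reader might infer an effect on DLT assessment, the MTD, the RP2D or some statistical result. The documents do not support this: the rules concern re-treatment after toxicity, and no figure in the plan depends on them.

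The conclusion rests on the cohort descriptions in Sections 1.3.2, 3.1.2 and 3.4 being complete. Cohorts 4A and 8A fall within named ranges without a stated tremelimumab dose, Section 1.6.4 mentions escalating tremelimumab doses, and Figure 1 could not be read in the copy reviewed. The 120 mg may be left over from a planned higher level; that is inference. The tally of 69 leaves no participant in such a cohort at that date. The documents do not say how many participants remain on treatment, so the number affected is unknown.

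**What to change.** In Section 5.4.4.2:

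- Replace the bracketed doses with: *reduced by 1 dose level per Table 3 (40 mg), or to an intermediate dose below the participant's current dose agreed with the sponsor*.
- Delete the one-week and Grade ≤2 route. Refer instead to Table 4 or Table 6 as applicable, and state that these take precedence over the general criteria in 5.4.2 where they are stricter.

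For Table 6 and Appendix 7:

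- State that where Table 6, including its double-asterisk footnote, and Appendix 7 differ, the more restrictive instruction applies. Permanent discontinuation under Appendix 7, including for myasthenia gravis and Grade 3 pneumonitis, then overrides the resumption allowance.
- Keep the Table 6 withholding for Grade 2 endocrinopathy, the sponsor discussion before resumption, and permanent discontinuation for myocarditis of any grade.

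This is a substantive safety change, so the cost is a protocol amendment with prospective IRB/EC approval (Section 12.1) and slightly more withheld doses. It adds no patients, visits or procedures.

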**Table 3. Tremelimumab Available Dose Levels**

Dose Level	Tremelimumab*
-1	40 mg
Starting	80 mg**

\* Intermediate doses may also be considered upon discussion with the sponsor.

\*\* Dose lower than 80 mg may be evaluated based on emerging safety data.

**Table 4. Dose Modifications for Tremelimumab Related Toxicity When Given in Combination with AdC68 or pDNA**

Toxicity	Grade 1/2	Grade 3	Grade 4
Non-hematologic	Continue at the same dose level.	Withhold dose until toxicity is Grade $\leq 1$ , or has returned to baseline, then resume treatment at the same dose level or reduce the dose by 1 level at the discretion of the investigator*.	Discontinue treatment.
Hematologic	Continue at the same dose level.	Withhold dose until toxicity is Grade $\leq 2$ , or has returned to baseline, then resume treatment at the same dose level.	Discontinue treatment.

\* Nausea, vomiting, or diarrhea must persist at Grade 3 despite maximal medical therapy to require dose modification.

#### 5.4.4.3. PF-06801591 Dose Reductions

Events including, but not limited to, pneumonitis, colitis, creatinine and liver function test (LFT) elevation should be monitored carefully with this class of agents. Changes in the dose levels for PF-06801591 may be allowed depending on the type and severity of toxicity encountered. Dose reductions may be required for PF-06801591, tremelimumab or potentially both compounds depending on the event and the severity. After a dose interruption, it is acceptable to resume dosing with the PrCa VBIR alone, and PF-06801591 treatment to resume at the next planned dosing. Dose reductions of PF-06801591 by 1 dose level may be allowed, including dose reductions below the starting dose. In addition an intermediate dose may be considered. All dose modifications/adjustments must be clearly documented in the participant's source notes and CRF.

**Table 5. PF-06801591 Available Dose Levels**

Cohort	Starting Dose*	Level -1**
3B	300 mg	130 mg
5B	130 mg	75 mg

\* The starting dose may be modified based on emerging safety data. See Section [Clinical PF-06801591 Dosing](#) for additional details.

\*\* Intermediate doses may also be considered upon discussion with the sponsor.

Table 5 describes the recommended dose modification for PF-06801591 treatment-associated toxicity. Algorithms for the management of suspected pulmonary, GI, liver, endocrine, skin, neurological and renal toxicities have been developed (See [Appendix 7](#)).

Participants requiring >2 weeks of dose interruption should be considered for discontinuation of treatment with PF-06801591. Participants may be allowed to resume dosing with the PrCa VBIR alone rather than in combination with PF-06801591 for one dose with plans to resume dosing with PF-06801591 at the next dosing timepoint if agreed upon by the investigator and sponsor. This would result in more than 2 weeks of dose interruption. Participants who discontinue PF-06801591 due to toxicity will be allowed to remain in the study and continue treatment with the other components.

The following serves as demonstrating general rules. Action may differ in specific cases based on evaluation by the investigator and the sponsor.

**Table 6. Dose Modifications for PF 06801591 and/or Tremelimumab (When Given in Combination With PF 06801591) Related Toxicity**

Toxicity	Grade 1	Grade 2	Grade 3	Grade 4
Non-hematologic	Continue at the same dose level.	For pneumonitis, endocrinopathy, colitis, creatinine, AST, ALT, or total bilirubin elevations, withhold dose until toxicity is Grade $\leq 1$ , or has returned to baseline, then resume at the same dose level or reduce by 1 level (considering each compound separately) at the discretion of the investigator.  For all other events, continue at the same dose level.	For pneumonitis, colitis, endocrinopathy, creatinine, AST, ALT or total bilirubin elevations, or pruritus discontinue treatment.**  For all other events withhold dose until toxicity is Grade $\leq 1$ , or has returned to baseline, then resume treatment at the same dose level or reduce the dose by 1 level (considering each compound separately) at the discretion of the investigator.* Treatment may resume with the PrCa VBIR with an interruption of PF-06801591 for one dose at the discretion of the investigator.	Discontinue treatment.**
Hematologic	Continue at the same dose level.	Continue at the same dose level.	Withhold dose until toxicity is Grade $\leq 2$ , or has returned to baseline, then resume treatment at the same dose level.	Discontinue treatment.**

\* Nausea, vomiting, or diarrhea must persist at Grade 3 despite maximal medical therapy to require dose modification.

\*\* For Grade  $>3$  colitis or pneumonitis, discontinue treatment permanently. For any grade of myocarditis discontinue treatment permanently. For all other conditions participants may remain in the study and resume therapy once toxicity has returned to Grade  $\leq 1$  or baseline, after discussion with the Sponsor.

## 5.5. Investigational Product Storage

The investigator, or an approved representative, eg, pharmacist, will ensure that all investigational products are stored in a secured area with controlled access under required storage conditions and in accordance with applicable regulatory requirements.

Upon receipt at the site, all drug product should be immediately transferred, in its original container, to the appropriate monitored storage area. Current storage conditions for AdC68 vials are frozen (-20°C $\pm$ 5°C). The current storage conditions for the pDNA, tremelimumab and PF-06801591 are refrigerated (2-8°C). Storage conditions stated in the single reference safety document (eg, Investigator's Brochure) will be superseded by the

storage conditions stated in the labeling. Please see the Instructions for Use for details on storage of the TDS-IM device.

Site systems must be capable of measuring and documenting (for example, via a log), at a minimum, daily minimum and maximum temperatures for all site storage locations (as applicable, including frozen, refrigerated and/or room temperature products). This should be captured from the time of investigational product receipt throughout the study. Even for continuous monitoring systems, a log or site procedure that ensures active daily evaluation for excursions should be documented. The operation of the temperature monitoring device and storage unit (for example, refrigerator), as applicable, should be regularly inspected to ensure it is maintained in working order.

Any excursions from the product label storage conditions should be reported upon discovery. The site should actively pursue options for returning the product to storage conditions as described in the labeling, as soon as possible. Deviations from the storage requirements, including any actions taken, must be documented and reported to the sponsor.

Once an excursion is identified, the investigational product must be quarantined and not used until the sponsor provides documentation of permission to use the investigational product. It will not be considered a protocol deviation if the sponsor approves the use of the investigational product after the temperature excursion. Use of the investigational product prior to sponsor approval will be considered a protocol deviation. Specific details regarding information the site should report for each excursion will be provided to the site.

## **5.6. Investigational Product Accountability**

All investigational product must be kept in a locked, limited access room. The investigational product and electroporation device must not be used outside of the context of this protocol. The investigator's site must maintain adequate records documenting the receipt, use, loss, or other disposition of the investigational product supplies. To ensure adequate records, all components of PrCa VBIR as well as PF-06801591 will be accounted for in the drug accountability inventory forms as instructed by the sponsor.

### **5.6.1. Destruction of Investigational Product Supplies**

The sponsor or designee will provide guidance on the destruction of unused investigational product (eg, at the site). If destruction is authorized to take place at the study site, the investigator must ensure that the materials are destroyed in compliance with applicable environmental regulations, institutional policy, and any special instructions provided by Pfizer, and all destruction must be adequately documented.

